**Document History:**

Version No.	Date	Chapter Attachment	/	Reason for Review / Modification
First draft	21.12.2023	n.a.		n.a.

## 1. Introduction

The aim of this project is to investigate the efficacy of open-label-placebo (OLP) treatment in reducing antidepressant discontinuation symptoms in remitted depressive disorder using a series of N-of-1 trials. This Statistical Analysis Plan (SAP) will provide more detailed description about the endpoints and corresponding analyses.

This study is part of a collaborative research center (CRC 289 Treatment Expectation: [www.treatment-expectation.de/en/](http://www.treatment-expectation.de/en/)).

### 1.1. Background

Discontinuation of antidepressant medication is associated with a broad range of physical and psychological symptoms, with an average incidence of 56% in fully remitted cases (Davies and Read 2019). Clinical trials indicate that the therapeutic effect of antidepressant medication over and above placebo is relatively small, in other words, placebo effects show a similar benefit as active antidepressants in antidepressant trials (Cipriani et al. 2018). Open-label-placebo (OLP) treatment appears to be effective for symptoms common during discontinuation of antidepressant medication such as pain, flu and fatigue (Wernsdorff et al. 2021). This study aims to investigate the efficacy of OLP in reducing antidepressant discontinuation symptoms through a series of N-of-1 trials. N-of-1 trials offer a pragmatic methodology for the proposed study as they require a smaller sample size compared to randomized controlled trials. Therefore, they are particularly suited for populations that are challenging to recruit (i.e., patients fulfilling the guideline criteria for discontinuation of their antidepressant medication) (Guyatt et al. 2000). They allow to obtain estimates of individual-level treatment effects and aggregating a series of N-of-1 trials allow for estimates population-level treatment effects (Zucker et al. 1997).

### 1.2. Overall Study Aims

Aim 1: To obtain individual-level and population-level effect estimates of the average efficacy of OLP relative to no treatment in reducing antidepressant discontinuation symptoms (primary outcome), and in improving dysfunctional treatment expectation, depressed mood, and anhedonia (secondary outcomes) based on a series of N-of-1 trials.

Aim 2: To explore factors that modify the efficacy of OLP, i.e., age, female sex, prior negative experiences with discontinuation, discontinuation symptom load over the discontinuation period and higher maintenance dose and longer duration of antidepressant use.

### 1.3. Study Endpoints

#### 1.3.1. Primary Endpoint

Discontinuation symptoms during the experimental phase (N-of-1 trials) are assessed twice daily for eight weeks (112 assessments) via a smartphone application ('StudyU') using the

Generic Rating Scale for Treatment Effects (GEEEACT) adjusted for the ambulatory assessment context (Konigorski et al. 2022; Rief et al. 2021). Discontinuation symptoms are rated on a 11-point numeric rating scale (NRS) ranging from 0-10. Higher scores indicate more severe discontinuation symptoms.

### 1.3.2. Secondary Endpoints

Treatment expectations during the experimental phase (N-of-1 trials) are assessed twice daily for eight weeks via the 'StudyU' application using an adjusted version of the Generic Rating Scale for Treatment Expectations (GEEEEXP) (Konigorski et al. 2022; Rief et al. 2021). Treatment expectations are rated on a 11-point NRS, with higher scores indicating expectation of more severe discontinuation symptoms until the next assessment. Depressed mood and anhedonia during the experimental phase are measured via the 'StudyU' application using the Patient-Healthcare-Questionnaire-2 (PHQ-2) consisting of 2 items adjusted to the ambulatory context (Kroenke et al. 2003). These are rated on a 4-point Likert scale, ranging from 0-3, with higher scores suggestive of a higher degree of depressive symptomatology.

### 1.3.3. Safety Endpoints

Major safety concerns for participants discontinuing their antidepressant medication include discontinuation symptoms, depressive symptoms, and adverse events (AEs). All safety endpoints are monitored throughout the study at (bi-)weekly study visits. Discontinuation symptoms are assessed with the Generic Rating Scale for Treatment Effects (GEEEACT) (Rief et al. 2021). Depressive symptoms will be monitored by self- and expert-rated depressive symptoms with the Beck Depression Inventory (BDI-II) and the Montgomery-Åsberg Depression Scale (MADRS) (Hautzinger et al. 2006; Davidson et al. 1986). AEs will be examined by a single safety question and classified according to the 'Common Terminology Criteria for Adverse Events' (CTCAE) (National Institutes of Health, National Cancer Institute 2009). In addition, the assessor evaluates the clinical impression of the participant.

## 2. Study Methods

### 2.1. Trial Design

This trial is a series of randomized, single-blinded, multicenter N-of-1 trials that compares OLP to no treatment in reducing antidepressant discontinuation symptoms. Treatment periods consist of 2-week periods of OLP and no treatment in an alternating order (i.e., ABAB/BABA), where 'A' represents OLP and 'B' no treatment. Participants will be randomized to either OLP or no treatment as their starting intervention and alternate between these two conditions during the eight-week experimental phase (N-of-1 trials). Results of the individual N-of-1 trials will be combined to estimate the average population-level efficacy of OLP compared to no treatment.

## 2.2. Randomization and Blinding

Patients will be randomized with a 1:1 ratio to the two conditions differing in treatment order (ABAB/BABA). The allocation sequence is based on computer-generated random numbers in R-Studio with the package *blockrand* using a block-randomization. Patients and study staff responsible for the randomization procedure will be unblinded to treatment allocation. Unblinded study staff are not involved in further assessments, except for the instructions of the treatment conditions. All other researchers involved in the assessments of the patients will be blinded to treatment allocation and patients are asked not to inform the assessor about the current condition.

## 2.3. Sample Size

Sample size are based on the main analysis concerning the aggregation of the N-of-1 trials to assess the average treatment efficacy of OLP compared to no treatment in reducing discontinuation symptoms assessed on a 11-point numeric rating scale GEEEACT (Rief et al. 2021). Sample size calculation was performed using the *Shiny-App* (<https://jiabeiyang.shinyapps.io/SampleSizeNof1/>) which implements a linear mixed model specifically designed for sample size calculations in a series of N-of-1 trials (Yang et al. 2021). We assumed a fixed intercept and random slope model for alternating sequences (ABAB/BABA). We used the daily GEEEACT scores for a fixed number of patients ( $N = 20$ ) and a fixed number of measurements per patient (112 measurements) with a standardized homogeneous residual error of 1.5, variance of random slope of 0.75, and an AR-1 structure for repeated measures with a correlation of 0.7 (conservative estimation). The results of the sample size calculation suggest that a sample size of 18 participants yields a power of 93% for identifying a mean difference between OLP treatment and no treatment when the mean difference is 0.8 points (on the GEEEACT 11-point numeric rating scale) which we consider as minimally clinically important difference (at a significance level of 5%). Considering possible dropout, we will recruit 20 patients into the study. This study design can be expected to yield naïve (i.e., non-pooled) estimates of the individual treatment effects with a standard error of about 0.3, hence allowing also meaningful inference on the individual level.

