#### **3.3.1. Analyses of Individual N-of-1 Trials**

At the end of the individual N-of-1 trials, statistical analyses will be applied to compare the outcomes of OLP vs no treatment. Bayesian models will be utilized to compare the average ratings of discontinuation symptoms (primary outcome) during the periods of OLP treatment periods to those with no treatment. These obtained estimates of individual-level effects can be viewed as naïve estimates as they do not incorporate information from the other participants. We will include a first-order autoregressive (AR1) error structure to acknowledge that measurements at adjacent times show a higher correlation than measurements far apart in time, given the longitudinal nature of our data. Non-informative priors will be selected for all parameters, as no prior information was available before the study that allowed a reasonable effect estimate of OLP treatment in reducing discontinuation symptoms. Separate analyses will be conducted for each individual to compare the average response to treatment. Based on this model, we will obtain estimates of the posterior distribution of the average OLP treatment effect in reducing discontinuation symptoms on an individual level. Secondary outcomes such as dysfunctional treatment expectations, depressed mood, and anhedonia will be analyzed similarly.

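### The individual-level standard error of about 0.3 in SAP section 2.3 does not follow from that section's own inputs, which give about 0.5 (if 1.5 is an SD) or 0.4 (if it is a variance)

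*SAP*

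**What the plan says.** The first part of Aim 1 (section 1.2) is "To obtain individual-level and population-level effect estimates of the average efficacy of OLP relative to no treatment", so individual estimates are a stated aim of the trial.

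Section 2.3 gives the planning inputs. Each patient contributes 112 measurements. The residual and slope terms are entered as "standardized homogeneous residual error of 1.5, variance of random slope of 0.75". For the dependence between ratings, the plan takes "an AR-1 structure for repeated measures with a correlation of 0.7 (conservative estimation"). It reports 93% power with 18 participants for a mean difference of 0.8 points, which it treats as the minimally important difference. The paragraph closes by saying the design will give naïve, non-pooled "estimates of the individual treatment effects with a standard error of about 0.3, hence allowing also meaningful inference on the individual level". No separate inputs and no derivation are given for that figure.

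The layout of the ratings comes from sections 1.3.1 and 2.1. Symptoms are "assessed twice daily for eight weeks (112 assessments"), and "Treatment periods consist of 2-week periods of OLP and no treatment in an alternating order". That makes four blocks of 28 ratings.

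Section 3.3.1 describes the individual analysis. The estimates are naïve because "they do not incorporate information from the other participants", and on the error structure it says: "We will include a first-order autoregressive (AR1) error structure".

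**The concern.** Positive autocorrelation of 0.7 within long treatment blocks reduces the information in 112 ratings considerably. A standard error of 0.3 is close to what 112 independent ratings with SD 1.5 would give, yet the same paragraph assumes strong correlation and calls that assumption conservative.

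The figure matters because it is the only planning support for the claim about individual-level inference, which the SAP derives from it directly. At a standard error of 0.3, one patient's 95% interval reaches 0.59 points either side, inside the 0.8-point minimally important difference. If the true precision is clearly worse, readers who judge individual results against the planned precision will over-interpret them.

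**Working it through.** **Inputs.** n = 112 ratings in four alternating blocks of 28 (sections 1.3.1 and 2.1); residual error 1.5, correlation ρ = 0.7, slope variance 0.75, N = 18, difference 0.8 (section 2.3). The 1.5 is read both ways: SD 1.5 (variance 2.25), or variance 1.5 (SD 1.225).

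**Step 1: do these inputs reproduce the stated power?** With SE the single-patient standard error from step 2, the population standard error is √((0.75 + SE²)/18). Power (normal approximation, two-sided 5%) is Φ(0.8/population SE − 1.96).
- SD reading: √((0.75 + 0.243)/18) = 0.235; power 92.6%.
- Variance reading: √((0.75 + 0.162)/18) = 0.225; power 94.5%.

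Both are close to the stated 93%, so the inputs are being read as the SAP intends. The power figure does not settle SD versus variance: with a t reference on 17 degrees of freedom the values are 89.4% and 91.7%, and the variance reading is then the nearer one.

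**Step 2: single-patient standard error under AR(1).** The model has an intercept and a treatment indicator z (ABAB; BABA gives the same result), with correlation 0.7^|i−j|. At unit residual variance the generalised least squares (GLS) information terms are:
- Intercept: (112 × 0.3 + 2 × 0.7)/1.7 = 35/1.7 = 20.588.
- Treatment: 1 + (54 × 0.3² + 2 × 0.7² + 1 × 1²)/0.51 = 1 + 6.84/0.51 = 14.412. The terms are the 54 steps within OLP blocks, two changes from OLP to no treatment, and one change back.
- Cross term: 1 + (54 × 0.09 − 2 × 0.3 × 0.7 + 0.3)/0.51 = 1 + 4.74/0.51 = 10.294.

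Information on the effect after estimating the intercept: 14.412 − 10.294²/20.588 = 14.412 − 5.147 = 9.265. The unit-variance standard error is 1/√9.265 = 0.3285.
- SD 1.5: 1.5 × 0.3285 = **0.493**.
- Variance 1.5: 1.225 × 0.3285 = **0.402**.

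The effective number of independent ratings is 4 × 9.265 ≈ 37, not 112.

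**Step 3: what would give 0.3?**
- Independent ratings: 2 × 1.5/√112 = 0.283 (SD), or 0.231 (variance).
- AR(1) with SE exactly 0.30 needs ρ of about 0.06 (SD) or 0.28 (variance). A second solution lies at a very high correlation, about 0.94 or 0.91. None is the planned 0.7.
- At ρ = 0.7, the residual SD would have to be 0.30/0.3285 = 0.913.
- Intercept treated as known: 1/√14.412 = 0.263, giving 0.395 (SD) or 0.323 (variance).
- Other variants move further away. A linear trend gives 0.53 or 0.43; 56 daily ratings give 0.575 or 0.47.

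**Step 4: consequence for one patient.** Half-width is 1.96 × SE. Detection is for a true effect of 0.8, two-sided 5%. The last column averages detection over slopes with mean 0.8 and variance 0.75.

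| SE | 95% half-width | Detection at 0.8 | Averaged over slopes |
|---|---|---|---|
| 0.30 (stated) | 0.59 | 76% | 66% |
| 0.402 (variance) | 0.79 | 51% | 55% |
| 0.493 (SD) | 0.97 | 37% | 47% |

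**The case against.** The best defence is that section 2.3 specifies a fixed-intercept, random-slope planning model. If 1.5 is a variance, and one intercept common to all patients is estimated jointly with a separate unpooled slope for each, the slope standard error is 0.327, which rounds to 0.3. On this view, non-pooled describes the treatment effects and not the intercept. The variance reading is plausible too, since the next input in the sentence is explicitly a variance.

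This shows how the figure might have arisen, but it does not make it right for the planned individual analysis. A shared intercept takes the patient's no-treatment level from other patients, and section 3.3.1 excludes that. Once the patient's own intercept is estimated, the standard error returns to 0.40. Under the SD reading, even the shared intercept gives 0.40.

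Four further points stand in part.
- The shortfall that holds on either reading is 0.40 against 0.3; the factor of 1.6 applies only if 1.5 is an SD.
- Section 3.3.1 plans posterior distributions with no test per patient, so the detection percentages only illustrate the loss of precision. Averaged over the planned slope distribution, the loss is also smaller.
- No sample size or analysis rule depends on the 0.3, and reported intervals will come from the data.
- That the figure came from ignoring autocorrelation is only an inference.

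**Conclusion.** The figure is wrong as written. For the individual model the SAP itself specifies, the planning inputs give a standard error of 0.49 (SD) or 0.40 (variance), 1.6 or 1.3 times the stated value. The expected single-patient 95% half-width is 0.97 or 0.79 points, so the claim about individual inference does not follow from the plan's own numbers.

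This assumes that all 112 ratings are present, that 0.7 is the correlation between adjacent ratings, that there is no time trend, and that non-informative priors make the posterior SD close to the GLS standard error. Missing ratings or a fitted linear trend would widen the interval.

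The 18-participant, 93% power statement and the analysis models are not affected. The point should be fixed, but it does not threaten the primary population-level conclusion.

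**What to change.** In section 2.3:
1. State whether the residual error of 1.5 is an SD or a variance.
2. Restate the individual standard error for the AR(1) model of section 3.3.1 at correlation 0.7: about 0.5 if an SD, about 0.4 if a variance.
3. Replace the closing claim about individual inference with the expected single-patient 95% interval, about ±1.0 or ±0.8 points respectively, set beside the 0.8-point minimally important difference.

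The cost is a small rewording of section 2.3 and a less favourable individual-level figure. Sample size, population power and analysis models stay as they are.

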## 2.4. Eligibility

### *Inclusion criteria*

- Adult patients ( $\geq 18$ ) meeting lifetime criteria for a major depressive disorder (MD) diagnosis, according to the Structured Clinical Interview for DSM-V (SCID-V-CV) (First et al. 2016);
- Current maintenance treatment with citalopram (20-40mg), duloxetine (60-100mg), escitalopram (10-20mg), paroxetine (20-40mg), sertraline (50-150mg), venlafaxine (75-150mg) or mirtazapine (30-45mg) with a constant dosage for 4 weeks;

- Discontinuation wish by participant supported by prescribing physician;
- Fulfilment of the S3 German national guideline recommendations to discontinue antidepressant medication: a) response to antidepressant medication; b) symptom remission  $\geq 4$  months (first episode) or  $\geq 2$  years ( $\geq 2$  episodes with significant functional impairment);
- Informed consent;
- Additional criteria for N-of-1 trial: At least moderate discontinuation symptoms after antidepressant discontinuation assessed by the Generic Rating Scale of Treatment Effects (GEEEACT score  $\geq 4$  during past week).

*Exclusion criteria*

- Current moderate or severe psychopathological symptoms or psychosocial impairments;
- Acute or chronic somatic illness which might interfere with depressive disorder, antidepressant or proposed study;
- Acute suicidality, psychotic symptoms, substance abuse, or addiction, current mania, or hypomania confirmed by SCID-V-CV or other psychopathology which might interfere with depressive disorder, antidepressant or proposed study;
- Any history of bipolar disorder or psychosis confirmed by SCID-V-CV;
- Severe stressful life events within 6 months prior to study participation;
- Current pregnancy;
- Insufficient German language proficiency.

## 2.5. Timing of Outcome Assessments

**Table 1:** Schedule of enrollment, intervention, and assessments according to SPIRIT-PRO

	STUDY PERIOD						
	Phase 1: Screening & Eligibility		Phase 2: Discontinuation		Phase 3: N-of-1 trials		Phase 4: Follow-up
Timepoint	S1	S2	T0	T1-T5	T6-T8	T9	FU1
Week	-2	-1	0	1/2/3/4/5	7/9/11	13	26
Enrolment:							
Eligibility screen	✓	✓					
Informed consent		✓					
Initial consultation							
prescribing physician		✓					
Allocation (N-of-1 trials)					✓ (T5)		
Interventions:							

Run-In (1 week)		↔				
Discontinuation phase (4 weeks)			↔			
N-of-1 trials (8 weeks)				↔		
Assessments:						
Primary outcome (‘StudyU’)						
Discontinuation symptoms (GEEE ACT )				↔		
Secondary outcomes (‘StudyU’)						
Treatment expectations (GEEE EXP )				↔		
Depressed mood and anhedonia (PHQ-2)				↔		
Effect modifiers (‘LimeSurvey’ and clinical interviews)						
Gender			✓			
Maintenance dose of antidepressant medication	✓					
Duration of antidepressant use	✓					
Prior negative experiences with discontinuation of antidepressant medication (GEEE PRE )*			✓			
Discontinuation symptom load over the discontinuation period (DESS)		✓	✓			
Other pre-specified outcomes (‘LimeSurvey’ and clinical interviews)						
Discontinuation symptoms (DESS)		✓	✓	✓	✓	✓
Current treatment effects (GEEE ACT )			✓	✓	✓	✓
Expert-rated depressive symptoms (MADRS+)*	✓	✓	✓	✓	✓	✓

Self-reported depressive symptoms (BDI-II)*	✓	✓	✓	✓	✓	✓
Recurrence			✓	✓	✓	✓
Well-being (SWEMWBS)		✓	✓	✓	✓	✓
Adherence (single item)		✓	✓	✓	✓	✓
Adverse events (single safety items)		✓	✓	✓	✓	✓
Treatment expectations (TEX-Q, GEEEEXP)*		✓	✓	✓	✓	✓
Psychopathology (SCID-5-CV)*	✓					
Demographic* & medical characteristics	✓	✓				
Anxiety vs. Depression (STADI Trait/State)*			✓			
Psychophysiological stress (PSS-10)*			✓			
Prior treatment experience (DESSPAST)			✓			
Side-effects of antidepressant medication (GASE)*			✓		✓	
Antidepressant medication blood serum level				✓ (T1)	✓	

*Note.* *S* = Screening; *T* = Treatment; *FU* = Follow-Up; *DESS* = Discontinuation Emergent Signs and Symptoms Scale; *GEEEACT* = Generic Rating Scale for Treatment Effects; *BDI-II* = Beck-Depressions-Inventory-II; *MADRS* = Montgomery-Åsberg Depression Rating Scale; *SWEMWBS* = Short Warwick-Edinburgh Mental Wellbeing Scale; *SCID-V-CV* = Structured Clinical Interview for DSM-V - Clinician Version; *STADI* = State-Trait Anxiety-Depression Inventory; *TEX-Q* = Treatment Expectation Questionnaire; *GEEEEXP* = Generic Rating Scale for Treatment Expectations; *GEEEPRE* = Generic Rating Scale for Previous Treatment Experiences; *GASE* = Generic Assessment of Side-Effects; *PHQ-2* = Patient-Health-Questionnaire-2; *PSS-10* = Perceived Stress Scale-10. \*Part of standardized psychometric test battery.

### 3. Statistical Analysis

#### 3.1. Trial Profile

A CENT (CONSORT extension (Shamseer et al. 2016)) flow diagram will display the flow of patients through the study. We will report the number of patients who (1) were assessed for

eligibility at screening\*, (2) were included in the study\*, (3) met the inclusion criteria for the N-of-1 trial\*, (4) allocated to each randomization sequence\*, (5) received the allocated treatment\*, (6) included in the primary analysis\*.

\*Reasons for exclusion will be provided

### **3.2. Baseline Characteristics of Patients**

Baseline characteristics of patients will be described including demographic parameters and medical characteristics. Categorical variables will be summarized by frequencies and percentages. Continuous variables will be reported by mean, standard deviation, minimum, maximum, or median and percentiles.

### **3.3. Analysis Principles for Final Analyses**

The primary analyses will provide individual-level and population-level estimates of the average efficacy of OLP treatment in reducing discontinuation symptoms based on the series of N-of-1 trials. This analysis will be based on the intention-to-treat population.

#### **3.3.1. Analyses of Individual N-of-1 Trials**

At the end of the individual N-of-1 trials, statistical analyses will be applied to compare the outcomes of OLP vs no treatment. Bayesian models will be utilized to compare the average ratings of discontinuation symptoms (primary outcome) during the periods of OLP treatment periods to those with no treatment. These obtained estimates of individual-level effects can be viewed as naïve estimates as they do not incorporate information from the other participants. We will include a first-order autoregressive (AR1) error structure to acknowledge that measurements at adjacent times show a higher correlation than measurements far apart in time, given the longitudinal nature of our data. Non-informative priors will be selected for all parameters, as no prior information was available before the study that allowed a reasonable effect estimate of OLP treatment in reducing discontinuation symptoms. Separate analyses will be conducted for each individual to compare the average response to treatment. Based on this model, we will obtain estimates of the posterior distribution of the average OLP treatment effect in reducing discontinuation symptoms on an individual level. Secondary outcomes such as dysfunctional treatment expectations, depressed mood, and anhedonia will be analyzed similarly.

